7.4.5. Myelofibrosis

[REDACTED]

[REDACTED]

[REDACTED]

[REDACTED]

[REDACTED]

[REDACTED]

[REDACTED]

[REDACTED]

[REDACTED]

[REDACTED]

[REDACTED]

[REDACTED]

[REDACTED]

[REDACTED]

[REDACTED]

[REDACTED]

[REDACTED]

[REDACTED]

[REDACTED]

[REDACTED]

[REDACTED]

[REDACTED]

[REDACTED]

[REDACTED]

[REDACTED]

[REDACTED]

[REDACTED]

[REDACTED]

[REDACTED]

[REDACTED]

[REDACTED]

[figure not shown]
[REDACTED]

[figure not shown]
[REDACTED]

[REDACTED]

[REDACTED]

[REDACTED]

8. PHARMACOKINETIC ANALYSES

The following PK parameters will be calculated from the blood plasma concentrations of INCB053914 using standard noncompartmental (model-independent) PK methods: C_{max} , t_{max} , C_{min} , AUC_{0-t} , and Cl/F . Pharmacokinetic calculations will be performed, if appropriate, using commercial software such as WinNonlin[®] (Pharsight Corporation, Mountain View, CA). Nominal times will be used in all cases, except when the difference between the actual time and nominal time is greater than 15 minutes for samples collected up to 4 hours after administration and greater than 30 minutes for samples collected more than 4 hours after administration; in these cases, actual time will be used for PK analysis.

If there is a sufficient amount of plasma concentration data from this study, the data will be analyzed by standard population PK methods using appropriate software (eg, NONMEM).

9. PHARMACODYNAMIC ANALYSES

Biomarker assessments in this study include the analysis of INCB053914 defined by pBAD promoter protein; [REDACTED]

Pharmacodynamics parameters will be summarized descriptively.

10. SAFETY AND TOLERABILITY

[Appendix A](#) provides a list of data displays.

10.1. General Considerations

Summary tables may be replaced with listings when appropriate. For instance, an AE frequency table may be replaced with a listing if it only contains a few unique PTs reported on relatively few subjects.

All AEs reported on the eCRF will be included in the summaries unless otherwise required by the study.

10.2. Adverse Events

10.2.1. Adverse Event Definitions

A TEAE is any AE either reported for the first time or worsening of a pre-existing event after first dose of study drug. Analysis of AEs (as discussed below) will be limited to TEAEs, but data listings will include all AEs regardless of their timing in relation to study drug administration.

Adverse events will be tabulated by MedDRA PT and SOC. Severity of AEs will be graded using the NCI CTCAE. The CTCAE version 4.03 is used for this study. The CTCAE reporting guidelines and grading details are available on the CTEP website.

The subset of AEs considered by the investigator to be related to study drug will be considered to be treatment-related AEs. If the investigator does not specify the relationship of the AE to study drug, the AE will be considered to be treatment-related. The incidence of AEs and treatment-related AEs will be tabulated. In addition, SAEs will also be tabulated.

Any missing onset date, causality, or severity must be queried for resolution. Unresolved missing causality and severity will be handled according to the following rules:

- An unresolved missing causality will be considered treatment-related.
- An unresolved missing severity will be identified as an unknown severity.

For purposes of analysis, all AEs will be considered TEAEs unless the AE can unequivocally be defined as not treatment emergent.

10.2.2. Dose-Limiting Toxicities

The number of subjects with DLTs and the type of DLT will be listed by dose level.

10.2.3. Maximum Tolerated Dose

In Part 1 and Part 3 of the study, the MTD will be defined as 1 dose level below that at which one-third of subjects or more in a particular cohort have DLTs.

10.2.4. Adverse Events of Special Interest

Adverse events of special interest include treatment-emergent ALT, AST, ALP, and bilirubin elevations and treatment-emergent AEs related to liver toxicities.

Number (%) of subjects reporting any treatment-emergent ALT, AST, ALP, and bilirubin will be summarized by grade. Any AEs related to liver toxicity will be identified using standard MedDRA queries.

10.2.5. Adverse Event Summaries

An overall summary of AEs by treatment group will include the following:

- Number (%) of subjects reporting any TEAEs
- Number (%) of subjects reporting any DLTs
- Number (%) of subjects reporting any SAEs
- Number (%) of subjects reporting any Grade 3 or 4 TEAEs
- Number (%) of subjects reporting any TEAEs related to INCB053914
- Number (%) of subjects reporting any TEAEs related to cytarabine
- Number (%) of subjects reporting any TEAEs related to azacitidine
- Number (%) of subjects reporting any TEAEs related to ruxolitinib
- Number (%) of subjects who temporarily interrupted INCB053914 because of TEAEs
- Number (%) of subjects who temporarily interrupted cytarabine because of TEAEs
- Number (%) of subjects who temporarily interrupted azacitidine because of TEAEs
- Number (%) of subjects who temporarily interrupted ruxolitinib because of TEAEs
- Number (%) of subjects who permanently discontinued INCB053914 because of TEAEs
- Number (%) of subjects who permanently discontinued cytarabine because of TEAEs
- Number (%) of subjects who permanently discontinued azacitidine because of TEAEs
- Number (%) of subjects who permanently discontinued ruxolitinib because of TEAEs
- Number (%) of subjects with INCB053914 dose reductions because of TEAEs
- Number (%) of subjects with cytarabine dose reductions because of TEAEs

- Number (%) of subjects with azacitidine dose reductions because of TEAEs
- Number (%) of subjects with ruxolitinib dose reductions because of TEAEs
- Number (%) of subjects who had a fatal TEAE
- Number (%) of subjects who withdrew from study because of an TEAE

The following summaries will be produced by MedDRA term (if 10 or fewer subjects appear in a table, a listing may be appropriate):

- Summary of TEAEs by SOC and PT
- Summary of TEAEs by PT in decreasing order of frequency
- Summary of TEAEs by SOC, PT, and maximum severity
- Summary of Grade 3 or 4 TEAEs by SOC and PT
- Summary of INCB053914 treatment-related AEs by SOC and PT
- Summary of cytarabine treatment-related AEs by SOC and PT
- Summary of azacitidine treatment-related AEs by SOC and PT
- Summary of ruxolitinib treatment-related AEs by SOC and PT
- Summary of Grade 3 or 4 INCB053914 treatment-related AEs by SOC and PT
- Summary of Grade 3 or 4 cytarabine treatment-related AEs by SOC and PT
- Summary of Grade 3 or 4 azacitidine treatment-related AEs by SOC and PT
- Summary of Grade 3 or 4 ruxolitinib treatment-related AEs by SOC and PT
- Summary of INCB053914 treatment-related AEs by SOC, PT, and maximum severity
- Summary of cytarabine treatment-related AEs by SOC, PT, and maximum severity
- Summary of azacitidine treatment-related AEs by SOC, PT, and maximum severity
- Summary of ruxolitinib treatment-related AEs by SOC, PT, and maximum severity
- Summary of TEAEs leading to death by SOC and PT
- Summary of treatment-emergent SAEs by SOC and PT
- Summary of treatment-emergent SAEs by PT in descending order of frequency
- Summary of treatment-emergent non-SAE by SOC and PT
- Summary of INCB053914 treatment-related SAEs by SOC and PT
- Summary of cytarabine treatment-related SAEs by SOC and PT
- Summary of azacitidine treatment-related SAEs by SOC and PT
- Summary of ruxolitinib treatment-related SAEs by SOC and PT
- Summary of TEAEs leading to INCB053914 dose reduction by SOC and PT
- Summary of TEAEs leading to cytarabine dose reduction by SOC and PT

- Summary of TEAEs leading to azacitidine dose reduction by SOC and PT
- Summary of TEAEs leading to ruxolitinib dose reduction by SOC and PT
- Summary of TEAEs leading to INCB053914 dose interruption by SOC and PT
- Summary of TEAEs leading to cytarabine dose interruption by SOC and PT
- Summary of TEAEs leading to azacitidine dose interruption by SOC and PT
- Summary of TEAEs leading to ruxolitinib dose interruption by SOC and PT
- Summary of TEAEs leading to discontinuation of INCB053914 by SOC and PT
- Summary of TEAEs leading to discontinuation of cytarabine by SOC and PT
- Summary of TEAEs leading to discontinuation of azacitidine by SOC and PT
- Summary of TEAEs leading to discontinuation of ruxolitinib by SOC and PT
- Summary of TEAEs of special interest by SOC and PT

10.3. Clinical Laboratory Tests

10.3.1. Laboratory Value Definitions

Laboratory values and change from baseline values will be summarized descriptively by visit. The baseline value will be determined using the nonmissing values collected before the first dose, prioritizing scheduled assessments for baseline identification over unscheduled visits. The last record before administration in the highest priority will be considered the baseline record. For baseline laboratory candidates with the same date and time in the same priority category, additional rules may be provided after consultation with the medical monitor to delineate which value will be defined as baseline.

Laboratory test values outside the normal range will be assessed for severity based on CTCAE grade or similar criteria where clinical intervention is required for CTCAE grading. The incidence of abnormal laboratory values and shift tables relative to baseline will be tabulated.

10.3.2. Laboratory Value Summaries

All test results and associated normal ranges from local laboratories will be reported in SI units. All tests with numeric values will have a unique unit per test. Any laboratory test results and associated normal ranges from local laboratories will be converted to SI units. For the limited number of cases where the associated normal ranges from a local laboratory cannot be obtained despite due diligence, if query is unsuccessful at resolving issue and analysis is mandatory, then the clinical scientist and medical monitor may provide a suitable normal range to be used in determining CTCAE grading to facilitate reporting the test results.

When there are multiple laboratory nonmissing values for a subject's particular test within a visit window, the convention described in [Table 9](#) will be used to determine the record used for by-visit tabulations and summaries.

Table 9: Identification of Records for Postbaseline By-Visit Summaries

Priority	Laboratory Visit	Proximity to Visit Window	Tiebreaker
1	Scheduled	In-window	Use smallest laboratory sequence number
2	Unscheduled	In-window	
3	Scheduled	Out-of-window	

Numeric laboratory values will be summarized descriptively in SI units, and non-numeric test values will be tabulated when necessary. In addition, line graphs will be provided for hemoglobin, platelet, WBC, and neutrophil counts.

For test results that will be summarized with available normal ranges, the number and percentage of subjects with the laboratory values being low (but never high), normal, high (but never low), and both low and high will be calculated for each test. This shift summary will be produced for each test for the safety population. The denominator for the percentage calculation will use the number of subjects in the baseline category (ie, low, high, normal, missing) as the denominator for the percentage in each of the categories during the treatment period.

For all gradable laboratory parameters, shift tables will be presented showing change in CTCAE grade from baseline to worst grade postbaseline for all treatment-emergent laboratory AEs. The number and percentage of subjects with normal laboratory values, and the laboratory values of Grade 1, 2, 3, or 4 will be calculated for each treatment group according to the largest treatment-emergent worsening of laboratory grade. Separate summaries for abnormally high and abnormally low laboratory values will be provided when the laboratory parameter has both high and low grading criteria. The denominator for the percentage calculation will be the number of subjects in the baseline category.

In cases where differentials of hematology parameters are obtained without corresponding absolute count data, efforts will be made to investigate if the conversion to an absolute value will lead to additional abnormalities. This will be discussed with the clinical team regarding appropriate documentation and action.

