3.3. Subject Exclusion Criteria

A subject who meets any of the following criteria will be excluded from the study:

1. Inadequate bone marrow function demonstrated by any of the following:

Laboratory Parameter	TGB (Part 1)	TGB (Part 2)	C-TGC (Parts 3 and 4)
Hemoglobin (g/dL)	< 8.0	< 8.0	Subjects unwilling to receive red blood cell transfusions to treat low hemoglobin levels are excluded.
Platelets ($\times 10^9/L$)	< 75	< 50	< 50 in 2 weeks before screening or platelet transfusions within 4 weeks of screening.
Absolute neutrophils ($\times 10^9/L$)	< 1.0	< 1.0	< 0.5 in the 2 weeks before screening.

Note: No specific hematologic exclusion criteria apply for TGA (Parts 1 and 2), Part 3 C-TGA and C-TGB, and Part 4 C-TGA E1 and C-TGB E1 cohorts.

CONFIDENTIAL

CONFIDENTIAL

2. Inadequate organ function demonstrated by any of the following, unless approved by the medical monitor:
 - Part 1 and Part 3
 - a. Total bilirubin > upper limit of normal (ULN; except total bilirubin > ULN is acceptable if direct bilirubin is $\leq 1.2 \times$ ULN. Subjects with Gilbert's syndrome who have total bilirubin $\leq 2 \times$ ULN may be enrolled with medical monitor approval).
 - b. AST or ALT > $1.5 \times$ ULN.
 - c. Creatinine clearance < 50 mL/min (< 30 mL/min for MM) based on Cockcroft-Gault formula or 24-hour urine analysis.
 - Part 2 and Part 4
 - d. Total bilirubin > ULN (except total bilirubin > ULN is acceptable if direct bilirubin is $\leq 1.2 \times$ ULN. Subjects with Gilbert's syndrome who have total bilirubin $\leq 2 \times$ ULN may be enrolled with medical monitor approval).
 - e. AST or ALT > $1.5 \times$ ULN.
 - f. Creatinine clearance < 40 mL/min (< 30 mL/min for MM) based on Cockcroft-Gault formula or 24-hour urine analysis.
3. Receipt of anticancer medications or investigational drugs within the following interval before the first administration of study drug (note: subjects enrolling in C-TGC must continue to receive their ruxolitinib throughout the study):
 - a. < 5 half-lives or 14 days, whichever is longer, for any investigational agent.
 - b. < 28 days for any antibodies or biological therapies.
 - c. < 5 half-lives for all other nonbiologic anticancer medications, or sponsor approval.
 - d. < 6 weeks for mitomycin-C or nitrosoureas.

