9.4.4.2. Clinical Laboratory Tests

Laboratory test values outside the normal range will be assessed for severity based on the normal ranges for the clinical reference laboratory. The incidence of abnormal laboratory values and shift tables relative to baseline will be tabulated.

Laboratory data will be classified into CTC grades for AEs (CTCAE v4.03). The following summaries will be produced for the laboratory data:

- Tables showing number and percentage of subjects with worst postbaseline CTC grade (regardless of baseline value) will be produced. Each subject will be counted only for the worst grade observed postbaseline.
- Shift tables using CTC grades to compare baseline with the worst postbaseline value will be produced with CTC grade.
- For laboratory parameters where CTC grades are not defined, shift tables to the worst postbaseline value will be produced using the low/normal/high classifications based on laboratory reference ranges.

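### SAP 10.3.2 omits the protocol's table of worst postbaseline CTC grade irrespective of baseline and counts grades by worsening, so, read literally, baseline Grade 4 and non-worsening Grade 3 subjects are not counted

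*SAP*

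**What the plan says.** Protocol 9.4.4.2 plans two separate CTC-grade outputs. The first is a plain count: "Tables showing number and percentage of subjects with worst postbaseline CTC grade (regardless of baseline value) will be produced". Its counting rule is "Each subject will be counted only for the worst grade observed postbaseline". The second is a comparison with baseline: "Shift tables using CTC grades to compare baseline with the worst postbaseline value will be produced with CTC grade".

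SAP 10.3.2 describes the graded output differently. For the shift tables it says "shift tables will be presented showing change in CTCAE grade from baseline to worst grade postbaseline for all treatment-emergent laboratory AEs". Subjects with normal values and with Grades 1 to 4 are counted by treatment group "according to the largest treatment-emergent worsening of laboratory grade". The denominator rule is "The denominator for the percentage calculation will be the number of subjects in the baseline category".

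SAP Appendix A lists CTC-grade shift summaries for hematology (Tables 3.3.3.1 to 3.3.3.4) and chemistry (Tables 3.3.6.1 to 3.3.6.4), but no table of worst grade irrespective of baseline. SAP Section 12 lists only the original version of the plan and records no departure from the protocol.

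The SAP does not define treatment-emergent for laboratory grades. The nearest definition is the one for adverse events in SAP 10.2.1: "either reported for the first time or worsening of a pre-existing event after first dose of study drug".

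On who may enter, the note to exclusion criterion 1 in Protocol 3.3 states "No specific hematologic exclusion criteria apply for TGA (Parts 1 and 2), Part 3 C-TGA and C-TGB", and goes on to name the Part 4 cohorts C-TGA E1 and C-TGB E1. The footnote to Protocol Table 4 describes cytopenias as expected in Part 1 TGA and the Part 3 combination groups.

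**The concern.** The two rules answer different questions. The protocol's table asks how many subjects were at Grade 3 or 4 at some point on treatment. The SAP's count asks how many got worse than they were before dosing. Both are useful and the protocol asks for both kinds of display, but the SAP text describes only the second.

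The rules diverge only for subjects who enter with severe abnormalities. The AML groups have no hematologic entry limits, so that is where the gap would appear. Laboratory evaluation is part of the primary safety endpoint in all parts (Protocol 2.2.1, SAP 2.3.1). The DLT definitions for Part 1 TGA and Part 3 C-TGA and C-TGB capture little cytopenia: anemia and febrile neutropenia do not apply, and Grade 4 neutropenia or thrombocytopenia counts only under a prolonged hypocellular-marrow condition (Protocol Table 4). The laboratory grade tables are therefore a main record of on-treatment marrow suppression in these groups.

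**Working it through.** The plan states no figure on this point, so there is none to reproduce. The check sets the two rules side by side and then sizes the difference.

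**Counting a subject by baseline grade** (worst postbaseline grade in the second column; SAP column read literally)

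| Baseline | Worst on treatment | Protocol table | SAP count |
|---|---|---|---|
| 0-2 | 3 or 4 | Grade 3-4 | Grade 3-4 |
| 3 | 4 | Grade 3-4 | Grade 3-4 |
| 3 | 3 | Grade 3-4 | not counted (no worsening) |
| 4 | 4 | Grade 3-4 | not counted (SAP grades stop at 4) |

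Only the last two rows differ.

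The wording of the shift tables may narrow them further. Under Protocol 8.1.1 a laboratory abnormality is an AE only if it causes signs or symptoms, is judged clinically meaningful, needs therapy, or leads to a change in study drug. A shift table confined to laboratory AEs could therefore leave out graded values that meet none of these conditions. The low/normal/high shift summary in the same SAP section covers the safety population with no such limit.

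**Size, over all subjects.** Inputs, none of them given in the documents:

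- b3, b4: shares of subjects at Grade 3 and Grade 4 at baseline.
- q: probability that a subject at Grade 2 or lower reaches Grade 3 or higher.
- w: probability that a baseline Grade 3 subject worsens to Grade 4.
- Baseline Grade 3-4 subjects are assumed to stay at Grade 3 or higher at least once postbaseline.

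Protocol rate = (1 - b3 - b4)q + b3 + b4.

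Literal SAP count over all subjects = (1 - b3 - b4)q + b3·w.

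Difference = b4 + b3(1 - w). It does not depend on q.

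Illustration with q = 0.8 and w = 0.5 (all assumed):

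| b3 = b4 | Protocol | SAP count over all subjects | Gap | Gap as w runs from 1 to 0 |
|---|---|---|---|---|
| 0% | 80% | 80% | 0 points | 0 |
| 10% | 0.8×0.8 + 0.2 = 84% | 0.64 + 0.05 = 69% | 15 points | 10 to 20 |
| 20% | 0.6×0.8 + 0.4 = 88% | 0.48 + 0.10 = 58% | 30 points | 20 to 40 |
| 30% | 0.4×0.8 + 0.6 = 92% | 0.32 + 0.15 = 47% | 45 points | 30 to 60 |

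**What the SAP would print.** Its denominators are baseline categories, so it gives row percentages and not the pooled figures in the third column. In the illustration, the rows for baseline Grade 2 or lower together show 80%, the baseline Grade 3 row shows 50% worsening, and the baseline Grade 4 row has nothing to count.

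**The case against.** The strongest reply is that nothing need be lost. Tables 3.3.3.x are titled as shifts in CTC grade to the worst abnormal value, in the safety population, with no mention of treatment emergence. The liver-function Tables 3.3.9.x do carry that term. If the shells are unrestricted, the Grade 4 to Grade 4 cell appears and the column totals reproduce the protocol's count. The sentence in SAP 10.3.2 also counts subjects with normal values, who by definition have not worsened, so it is loosely worded and may not be meant to drop non-worseners. Appendix A is offered as a guideline, and the SAP never says that it withdraws the protocol's table. Where disease itself causes cytopenia, counting worsening is a sound way to separate drug from disease effect.

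Much of this is fair. The shells are not in the documents, so the loss cannot be confirmed from the outputs, and treatment-emergent counting is a legitimate display. None of it restores the missing table: the protocol asks for the unconditional count as well, and the SAP text, as written, restricts what is shown.

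A reader might go further and infer that every AML subject entering with a Grade 3-4 cytopenia drops out. The documents do not support that, because a Grade 3 subject who reaches Grade 4 is counted under both rules.

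A reader might also take the gaps of 10 to 60 points as the understatement in a reported SAP rate. The SAP defines no such pooled rate. In the illustration, the protocol's 84%, 88% and 92% would stand beside an 80% row figure for subjects at Grade 2 or lower, a difference of 4, 8 and 12 points. Subjects entering at Grade 3-4 stay in the denominators of their own rows.

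Nor do dose or efficacy decisions turn on this: DLTs and the MTD follow Protocol Table 4, and the Part 4 test uses ORR. Baseline cytopenia also remains visible in the low/normal/high shift tables and the laboratory listings.

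**Conclusion.** The concern holds as an unrecorded mismatch between protocol and SAP on a component of the primary safety endpoint. The protocol's table of worst grade irrespective of baseline is absent from SAP 10.3.2 and Appendix A. Under the literal SAP wording, baseline Grade 4 subjects and non-worsening baseline Grade 3 subjects are not counted as Grade 3-4 on treatment. The effect is greatest in TGA, C-TGA and C-TGB.

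Expressed over all subjects, the shortfall is b4 + b3(1 - w). The formula rests on the assumption that baseline Grade 3-4 subjects remain at Grade 3 or higher at least once after baseline. With no subject entering at Grade 3-4 it is zero; its actual size cannot be stated, because the documents give neither the baseline grade distribution nor the probability of worsening. The point concerns how laboratory toxicity is reported, not dose selection or the efficacy test. It should be corrected because the remedy is cheap and the protocol already calls for the table.

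**What to change.** In SAP 10.3.2 and Appendix A, for each part:

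1. Add the protocol's table: number and percentage of subjects by worst postbaseline CTC grade irrespective of baseline, each subject counted once, with all subjects having a postbaseline value as denominator.
2. State that the CTC shift tables include all such subjects, whether or not they worsened and whether or not the value was reported as an AE.
3. Keep treatment-emergent worsening as a separate, clearly labelled display, and define the term for laboratory grades.

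The cost is some wording and one extra table or column per part, with no new data collection. The drawback is that reported hematologic Grade 3-4 rates will be higher and will include cytopenia present before dosing, so the table should be read beside the shift and treatment-emergent displays.
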